reduction (75%) in recurrent VTE as low-intensity rivaroxaban (10 mg daily) compared with low-dose aspirin (2). The 75% relative risk reduction was reported specifically for recurrent VTE and in the provoked VTE patient population, comparing rivaroxaban 10 mg daily versus low-dose aspirin. This relative risk reduction specifically pertains to our primary study outcome and our exact patient population and comes from a robust randomized controlled trial analysis. If anything, the reduction in the proposed study should be even greater since we propose a placebo-control instead of active (aspirin) control and we will be following our patients for 12 months, instead of allowing shorter follow-up as was reported in EINSTEIN CHOICE. Accordingly, assuming an estimated incidence in the placebo group of 6% at 12 months and a decrease in the primary outcome of 75% with apixaban 2.5 mg twice daily as compared with placebo, we calculated that we would need to enroll 279 patients in each group for the study to have 80% power to show the superiority of low-intensity apixaban over placebo, at a two-sided alpha level of 0.05. To account for patients who may be lost to follow-up or withdraw from the study, we will recruit 300 in each arm and 600 total.

EINSTEIN-CHOICE enrolled patients after a required 6 to 12 months of anticoagulant therapy. Our study requires that patients complete at least 3 months of anticoagulant therapy in accordance with current and widely-accepted evidence-based clinical practice guidelines (Eur Heart J. 2020; 41: 543–603, Chest. 2016;149:315-352, and Circulation. 2011;123:1788–1830). Data from the PADIS-PE study showed that the rate of VTE recurrence is higher closer in temporal proximity to the initial event, such that the recurrence rate is higher at 3-6 months after diagnosis than it is at 6-12 months (Couturaud F, et al. Six Months vs Extended Oral Anticoagulation After a First Episode of Pulmonary Embolism. JAMA. 2015;314(1):31-40). Accordingly, the anticipated event rate should be higher in our study than EINSTEIN-CHOICE and the resultant observed relative risk reduction is likely to be higher.

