Baseline characteristics will be summarized by group. Any imbalances between the treatment groups for any demographic or baseline characteristic will be assessed based on clinical relevance in reviewing the summaries. For any differences deemed clinically relevant to the efficacy comparisons, exploratory analyses that include the imbalanced factor as a categorized covariate will be performed.

To account for the effect of baseline low-dose aspirin use in the study population on the rate of recurrent VTE after an initial provoked event, we will perform a pre-specified stratified efficacy analysis of patients receiving low-dose apixaban or placebo with low-dose aspirin compared with patients just receiving low-dose apixaban or placebo. We will calculate stratum-specific risk ratios (RR). Comparing the “crude” (overall or unadjusted) and stratum-specific risk ratios will enable us to determine whether aspirin modifies the effect of low-dose apixaban and to what extent. If the stratum-specific risk ratio is similar to the crude risk ratio, then there is minimal impact of low-dose aspirin. However, if the stratum-specific risk ratio differs from the unadjusted estimate by 10% or more, then low-dose aspirin modifies the effect of low-dose apixaban. We will conduct a similar analysis for the safety outcome of major bleeding.

We will also pre-specify subgroup analyses focused on the safety and efficacy of major populations of interest, in particular, elderly patients (age \geq 65 years), women, and those with persistent provoking factors of immobility, obesity, heart failure, chronic lung disease, chronic kidney disease, hemodialysis, chronic inflammatory/autoimmune disorder, and atherosclerotic cardiovascular disease.

Means, medians, and frequency distributions will be calculated for continuous variables. Number and percentages will be reported for binary and categorical variables. Differences between subgroups of interest will be examined using the chi-square or Fisher's exact test for binary and categorical variables and t-test or Wilcoxon Rank Sum for continuous variables (if the subgroups are of sufficient size for statistical comparison).

Safety outcome analyses will be performed among patients who received one or more doses of a study drug (Safety Population). All p-values reported will be two-sided. A p-value < 0.05 will be considered significant. All analyses will be performed using SAS software.

Interim Analysis

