6.4.2 Subgroup Analysis

The study will conduct subgroup analyses based on certain predetermined factors such as whether the patient has PE versus non-PE, age (65 years or older versus younger), sex (male versus female), chronic kidney disease (defined as presence or absence of eGFR<60 mL/min/1.72m²), atherosclerotic cardiovascular disease (present versus absent), baseline low-dose aspirin use (present versus absent), the number of provoking risk factors (2 or more versus less than 2), provoking factor of travel, and baseline aspirin use. The survival analysis within each subgroup will be repeated using the main cohort and tested in confirmatory cohorts, as needed. The p-value of the additive interaction effect between treatment and subgroup will be reported.

In case the subgroup analysis of baseline aspirin use indicates a relevant modification effect (the p-value for the additive interaction effect <0.05), the study will repeat the primary analysis by reporting the treatment effect of apixaban vs placebo with the adjustments for a) the use of aspirin and b) the interaction term.

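### The protocol's 10% rule for aspirin effect modification would usually declare modification of the VTE effect when there is none, and the SAP's different criterion does not withdraw it

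*Combined protocol and SAP*

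**What the plan says.** The aspirin analysis is in the final protocol (11/19/2021), Statistical Methods, under Statistical Analysis Plan. It splits patients by baseline low-dose aspirin use and states the purpose: "Comparing the “crude” (overall or unadjusted) and stratum-specific risk ratios will enable us to determine whether aspirin modifies the effect of low-dose apixaban". The decision rule follows. A stratum ratio close to the crude one means minimal impact of aspirin; one that "differs from the unadjusted estimate by 10% or more, then low-dose aspirin modifies the effect of low-dose apixaban". The protocol then adds: "We will conduct a similar analysis for the safety outcome of major bleeding".

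The separate SAP (03/24/2025), section 6.4.2, lists baseline aspirin use as a subgroup and reports an interaction p-value. It treats modification as relevant when "the p-value for the additive interaction effect <0.05", and in that case repeats the primary analysis adjusted for aspirin and the interaction term. It neither repeats the 10% rule nor withdraws it.

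**The concern.** The protocol rule draws a firm conclusion from a point estimate alone. The trial expects about 22 VTE events, which the rule divides over two arms and two aspirin strata. Ratios built on so few events scatter far more than 10% by chance, so the rule responds mainly to noise.

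The final plan therefore holds two criteria for one question, and they will usually disagree. If the protocol rule is applied or reported, readers could be told that apixaban works differently with aspirin when the data do not show it. The protocol expects many participants to be on aspirin, so the statement would be noticed. If neither criterion is named as governing, the choice can be made after the results are known.

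**Working it through.** **Inputs.** From the protocol's Sample Size Calculation: "assuming an estimated incidence in the placebo group of 6% at 12 months", "a decrease in the primary outcome of 75% with apixaban 2.5 mg twice daily as compared with placebo" (so 1.5% on apixaban), two-sided alpha 0.05, and 300 recruited per arm. Randomization is 1:1, with no stratification by aspirin stated. The aspirin share is not given. The protocol says only that many patients will take aspirin and caps atherosclerotic disease as a qualifying factor at 35% per group. I assume shares of 10% to 50%.

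**The plan's own figure.** The protocol states "279 patients in each group for the study to have 80% power". With mean rate 0.0375:

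n = [1.960 × √(2 × 0.0375 × 0.9625) + 0.842 × √(0.06 × 0.94 + 0.015 × 0.985)]² / (0.045)² = (0.5266 + 0.2245)² / 0.002025 = 278.6, so 279 per group, with power 0.8005. The inputs reproduce the plan.

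**Expected VTE events.** Placebo 300 × 0.06 = 18; apixaban 300 × 0.015 = 4.5; total 22.5. In the apixaban arm's aspirin stratum the expectation is 4.5 × share: 0.45 at 10% and 2.25 at 50%.

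**Approximation by hand, 30% share, aspirin stratum only, true RR 0.25 in both strata.** For a fraction w of each arm, the variance of log RR is

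v(w) = 1/(300w × 0.015) + 1/(300w × 0.06) − 2/(300w).

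- v(0.3) = 0.741 + 0.185 − 0.022 = 0.904
- v(1) = 0.222 + 0.056 − 0.007 = 0.271
- The crude log RR is close to the weighted mean of the stratum values, so the SD of log(stratum RR / crude RR) is √(0.904 − 0.271) = 0.795.
- The rule stays silent only between ln 0.9 = −0.105 and ln 1.1 = 0.095. That probability is Φ(0.120) − Φ(−0.132) = 0.100, so the rule flags about 90%.

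**Simulation.** 200,000 trials per share, 300 per arm, 6% vs 1.5%, RR 0.25 in both strata, random stratum sizes. A trial is evaluable if both stratum ratios are defined and the crude ratio is defined and not zero. Percentages of evaluable trials flagged:

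| Aspirin share (assumed) | Either stratum, 10% relative | Both strata, 10% relative | Either stratum, 0.10 absolute |
|---|---|---|---|
| 10% | 97.7 | 62 | 86 |
| 20% | 94.1 | 75 | 74 |
| 35% | 90.4 | 81 | 59 |
| 50% | 88.6 | 83 | 53 |

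Combining the two narrower readings (both strata, each by 0.10 absolute) gives 6% to 37% over the same shares in the same simulation.

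**Sensitivity, either stratum, 10% relative.**
- Undefined ratios counted as not flagged: 86.5% to 92.1%.
- 279 per arm: 89.2% to 97.9%.
- Aspirin itself lowering VTE risk by 33%, a figure in the protocol: 89.5% to 96.1%.
- Placebo rate 11.1%, the protocol's registry figure: 82.9% to 90.2%.
- Ten times the sample: still about 69% by the hand formula at a 30% share.

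**Comparison.** A Wald test of the ratio of the two stratum risk ratios at p < 0.05 flags about 1.0% to 1.8% of the same null trials. It stands in for the SAP's Cox-based interaction test and is conservative because events are few.

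**Major bleeding.** The protocol's Introduction and Background gives 0.3% to 0.5% in the rivaroxaban-versus-aspirin extension trial. With 300 per arm and no modification, at 0.3% vs 0.4% and at 0.5% vs 0.5%:
- a usable crude ratio exists in about 42% to 60% of trials;
- the rule can be fully evaluated in about 3% to 22%;
- where it can, it flags 90% or more, which is about 3% to 20% of all trials.

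**The case against.** The strongest reply is that the SAP has overtaken the rule. It is later, and it replaces the risk-ratio framework with time-to-event outcomes, log-rank tests and hazard ratios. Its table of analysis sets lists no risk ratios, and it gives the aspirin question its own criterion and consequence. An analyst who follows the SAP would not compute the 10% comparison. This limits the harm to the case where the protocol rule is applied or reported. It does not remove the conflict, because neither document says that one criterion replaces the other.

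A reader might infer that the rule is even worse for bleeding and that the trial would report altered bleeding risk whatever the truth. The documents' own rates do not support that: at 0.3% to 0.5% the rule usually cannot be evaluated.

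A reader might also infer that the SAP leaves major bleeding to the 10% rule because 6.4.2 does not name it. That is not established either. SAP 6.4.1 defines the survival analysis for safety as well as efficacy outcomes, and 6.4.2 repeats that analysis within subgroups. Read together, they arguably cover bleeding already.

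Finally, the size depends on the reading. The protocol does not say whether one or both strata must differ, or whether 10% is relative or absolute. The relative, either-stratum reading is the natural one. The narrower readings lower the figure, and only the two together bring it near conventional error rates, and then only at a low aspirin share.

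**Conclusion.** The 10% rule is unsound as written. For recurrent VTE with no true modification it flags at least one stratum in about 89% to 98% of evaluable trials. The figure is 62% to 83% if both strata must differ and 53% to 86% if the difference is 0.10 absolute. These figures rest on the plan's 6% and 75% assumptions, 300 per arm, and an assumed aspirin share of 10% to 50%. For major bleeding the accurate statement is that the rule is mostly not evaluable, and misleading when it is.

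It does not follow that the trial will report a false aspirin interaction, since the SAP sets a different criterion for the same question. What stands is an unsound rule left in the final protocol and two unreconciled criteria. Severity is minor: this is a secondary effect-modification question, and the primary superiority test, sample size and stopping rules are unaffected.

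**What to change.** Delete the 10% sentence from the protocol's aspirin analysis. State that the treatment-by-aspirin interaction test in SAP 6.4.2 replaces it for recurrent VTE and, by name, for major bleeding where events allow. Show stratum estimates with confidence intervals descriptively. Add that a non-significant interaction is not evidence of no modification, because with about 22 VTE events, and fewer bleeds at the cited rates, power is low.

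The cost is one short amendment to the two documents, with no new data and no change to the primary analysis.

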Inclusion criteria (all must be checked)	
 Age \geq 18 years  Objectively-confirmed DVT and/or PE  Treated for at least 3 months with standard therapeutic anticoagulant therapy  Has not suffered symptomatic recurrence during prior anticoagulant therapy  Outpatient follow-up at BWH  Willing to provide written informed consent
 
AND have at least one of the following persistent provoking VTE risk factors:
 
 Persistent immobility (defined as paralysis, other inability to ambulate freely, bed-bound, wheelchair-bound)  Obesity (defined as BMI \geq 30 kg/m²)  Heart failure (systolic, diastolic, or combined)  Chronic lung disease (COPD, asthma, interstitial lung disease)  Chronic kidney disease (eGFR <60 mL/min/1.72m²)  Chronic inflammatory/autoimmune disorder (inflammatory arthritis, vasculitis, inflammatory bowel disease, chronic infection)  Atherosclerotic cardiovascular disease (coronary, cerebrovascular, or peripheral artery disease) (up to 35% in each study group may have atherosclerotic cardiovascular disease as a qualifying persistent risk factor)

Exclusion criteria (NONE must be checked)	
 Women who are pregnant or breastfeeding  Women of child-bearing potential who are unwilling or unable to use an acceptable method of birth control (such as oral contraceptives, other hormonal contraceptives [vaginal products, skin patches, or implanted or injectable products], or mechanical products such as an intrauterine device or barrier methods [diaphragm, condoms, spermicides]) to avoid pregnancy for the entire study  Active cancer within the past 5 years  Contraindication to antithrombotic or antiplatelet therapy  Requirement for ongoing anticoagulant therapy (including atrial fibrillation with a CHADS_{VASC} >1, diagnosed antiphospholipid antibody syndrome/deficiency of protein C,

	
S, or antithrombin), dual antiplatelet therapy, P2Y12 inhibition, or aspirin at a dose of >81 mg daily
 
[] Hemoglobin level < 9 mg/dL, a platelet count < 100,000/mm³, a serum creatinine level > 2.5 mg/dL, an ALT or AST level > 2 times the upper limit of the normal range, or a total bilirubin level > 1.5 times the upper limit of the normal range
 
[] History of a platelet disorder such as Von Willebrand Disease
 
[] History of bleeding diathesis or have had recent active bleeding
 
[] Active hepatobiliary disease
 
[] More than 6 months that have elapsed without taking an anticoagulant or low-dose aspirin
 
[] Known severe thrombophilia (any increased titer antiphospholipid antibody or positive lupus anticoagulant/DRVVT or deficiency of antithrombin, protein C, or protein S)
 
[] Life expectancy < 12 months or hospice care
 
[] Prisoners or subjects who are involuntarily incarcerated
 
[] Subjects who are compulsorily detained for treatment of either a psychiatric or physical (e.g., infectious disease) illness
 
[] Receiving concurrent non-FDA-approved or investigational agents or has received an investigational agent within the past 30 days prior to the first dose of study treatment (with the exception of approved medications being used for an approved indication, e.g., investigating a new dosing regimen for an approved indication).
 
[] Any condition, which in the opinion of the investigator, would put the subject at an unacceptable risk from participating in the study
 
[] Any other medical, social, logistical, or psychological reason, which in the opinion of the investigator, would preclude compliance with, or successful completion of, the study protocol

STOP HERE AND DO NOT ENROLL PATIENT IF ANY OF THE INCLUSION CRITERIA ARE ABSENT OR ANY EXCLUSION CRITERIA ARE PRESENT
	
Eligible	[] Yes [] No
Written informed consent signed	[] Yes [] No

Patient Demographics	
Study ID number	-----
Date of enrollment	____ / ____ / ____ MM DD YYYY
Date of birth	____ / ____ / ____ MM DD YYYY
Gender	 Male  Female
Ethnicity	 Hispanic/Latino  Non-Hispanic/Non-Latino
Race	 American Indian or Alaskan Native  Asian  White  Hispanic or Latino  Native Hawaiian or Pacific Islander  Black or African-American  Mixed race  Other, specify: _____
BMI calculated	_____ (kg/m ²)

Venous Thromboembolism Characteristics***	
***Patient may have both PE and DVT; if so complete both fields	
Deep Vein Thrombosis	DVT confirmed by imaging (ultrasound, CT, MRI, or venogram)  Yes  No
	Date of imaging diagnosis ____ / ____ / ____ MM DD YYYY
	Site of DVT  Upper extremity  Pelvic vein  Leg  Proximal with calf  Proximal without calf  Calf only

	[] Other (describe): _____
Pulmonary Embolism	PE confirmed by:  Ventilation perfusion scan  Chest CT  Contrast pulmonary angiogram Hypotension, shock, cardiac arrest or respiratory failure as presenting sign of PE:  Yes  No RV dysfunction  Yes  No Diagnosed by:  CT  Echocardiogram Positive cardiac biomarker (troponin or BNP)  yes  no
	Date of imaging confirmed diagnosis _____ / _____ / _____ MM DD YYYY
	Both PE and DVT present  Yes  No
	Symptomatic DVT or PE  Yes  No
	Advanced therapy for VTE  Inferior vena cava filter  Thrombolytic therapy for PE  Catheter thrombectomy for DVT  Catheter direct therapy for PE  Surgical thrombectomy for DVT  Surgical embolectomy for PE
	Outpatient VTE treatment history  LMWH monotherapy  Fondaparinux  Direct oral anticoagulant  Warfarin Duration of anticoagulation: _____ months (enter number out to the tenth place and round-up; for example 3.48 months would be 3.5 months)

Persistent Provoking VTE Risk Factors	
Persistent provoking VTE risk factors (patient must have at least one but can have multiple; record all that apply)	 Persistent immobility (defined as paralysis, other inability to ambulate freely, bed-bound, wheelchair-bound)  Obesity (defined as BMI ≥ 30 kg/m ²)  Heart failure (systolic, diastolic, or combined)  Chronic lung disease (COPD, asthma, interstitial lung disease)  Chronic kidney disease (eGFR <60 mL/min/1.72m ²)  Chronic inflammatory/autoimmune disorder (inflammatory arthritis, vasculitis, inflammatory bowel disease, chronic infection)  Atherosclerotic cardiovascular disease (coronary, cerebrovascular, or peripheral artery disease) (up to 35% in each study group may have atherosclerotic cardiovascular disease as a qualifying persistent risk factor)

VTE Risk Factors and Comorbid Conditions	
Cardiovascular disease	 Cardiomyopathy/diminished left ventricular systolic function If yes, EF (%) _____  Heart failure with reduced EF  Heart failure with preserved EF (EF >50%)  Coronary artery disease If yes,  Prior CABG  Prior coronary stent(s)  Prior MI  History of unstable angina  Stable angina  Valvular heart disease  Atrial fibrillation or atrial flutter  Pulmonary hypertension
Hypertension	 Yes  No
Peripheral artery disease	 Yes  No

Carotid occlusive disease	 Yes  No
Prior cerebrovascular accident (strokes or TIAs)	 Yes  No
Family history of VTE	 Yes  No
Prior personal history of VTE (other than the event that made the patient eligible for this trial)	 Yes  No
Hypercholesterolemia	 Yes  No
Chronic liver disease (as noted in chart)	 Yes  No If yes, cirrhosis  yes  no
Cigarette smoking (check only 1)	 Current smoker  Former smoker  Never smoker
Major surgery within 3 months of VTE diagnosis	 Yes  No If yes, date MM / DD / YYYY
Prior hospitalization within 30 days of VTE diagnosis	 Yes  No
Chronic lung disease (COPD, asthma, pulmonary fibrosis, interstitial lung disease)	 Yes  No
Diabetes mellitus	 Yes

(Type I or II)	[] No	
Inflammatory arthritis (rheumatoid arthritis, psoriatic arthritis)	[] Yes	[] No
Inflammatory bowel disease (Crohn's Disease, Ulcerative Colitis)	[] Yes	[] No
Inherited thrombophilia	[] Yes	[] No If yes, indicate: [] Factor V Leiden (heterozygous or homozygous) [] Prothrombin gene mutation (heterozygous or homozygous)
Active use of oral contraceptive or hormone replacement at time of VTE diagnosis	[] Yes	[] No
Infectious illness requiring antibiotics or antiviral therapy within 3 months of VTE diagnosis	[] Yes	[] No
Serum creatinine >2.5 mg/dL	[] Yes [] No If yes, is patient on dialysis? [] Yes [] No	If yes, patient should not be enrolled.
Concomitant medications	 aspirin If yes, dose = ____ mg/daily If >81 mg/daily, patient should not be enrolled.  daily NSAID use	

Study Treatment Characteristics	
Randomization	 Oral Apixaban 2.5 mg twice daily  Oral placebo twice daily
Date study drug started	 /  /  MM DD YYYY
Date study drug stopped	 /  /  MM DD YYYY Completed full 12 months of study drug?  Yes  No If did not stay on drug for 12 months, reason why not?  Fulfilled criteria for a primary study outcome (recurrent VTE or major/clinically relevant non-major bleed)  Patient expired  Adverse drug event or side-effect  Change in clinical status (such as change in goals of care, comfort measures, hospice care)  Patient preference/withdrawal of consent
Medication adherence (via pill count)	Total doses taken/total doses prescribed = ( / 720) x 100 =  %

12-Month Study Outcomes	
Deep vein thrombosis	 Yes  No If yes, date  /  /  MM DD YYYY Confirmed by diagnostic imaging:  Yes  No If yes, by?  Ultrasound  CT  MRI  Venography

	
Location:
 
 Upper extremity
 
If checked:
 
 Bilateral or SVC
 
 Lower extremity
 
If checked:
 
 Bilateral or IVC
 
 Proximal (popliteal or higher)
 
 Calf
 
Hospitalized?
 
 Yes
 
 No
 
Treatment:
 
 Anticoagulation
 
 Pharmacomechanical (catheter-based) therapy
 
 Surgery
 
 IVC filter

Superficial vein thrombosis	
 Yes
 
 No
 
If yes, date _____ / _____ / _____ MM DD YYYY

Other venous thrombosis (mesenteric, cerebral sinus, gonadal, etc.)	
 Yes
 
 No
 
If yes, date _____ / _____ / _____ MM DD YYYY

Pulmonary embolism	
 Yes
 
 No
 
If yes, date _____ / _____ / _____ MM DD YYYY
 
Confirmed by diagnostic imaging:
 
 Yes
 
 No
 
If yes, by?
 
 CT
 
 MRI

	
 Pulmonary angiography  V/Q scan
 
Location:  Unilateral  Bilateral
 
RV dysfunction on echocardiogram or CT?  Yes  No
 
Positive cardiac biomarker?  Yes  No
 
Associated with hemodynamic or respiratory instability (respiratory failure, shock, hypotension, cardiac arrest)?  Yes  No
 
Fatal?  Yes  No
 
Hospitalized?  Yes  No
 
Treatment:  Anticoagulation  Systemic fibrinolysis  Pharmacomechanical (catheter-based) therapy  Surgical embolectomy  IVC filter

Death	
 Yes  No
 
If yes, date _____ / _____ / _____ MM DD YYYY
 
Cause of death:  PE  Myocardial infarction  Stroke

	
 Other cardiovascular  Cancer-related  Non-cardiovascular, non-cancer  Unknown
 
 CV Death: includes death due to PE, MI, stroke, other cardiovascular cause, or unknown

Major or clinically relevant non-major bleed	
 Yes  No
 
If yes, date   /   /   MM DD YYYY

Major bleed	
 Yes  No
 
If yes, date   /   /   MM DD YYYY
 
Location:
 
 Intracranial  Surgical/operative site  Gastrointestinal  Genitourinary  Retroperitoneal  Pericardial  Pulmonary  Other thoracic  Musculoskeletal  Nasopharyngeal  Hematocrit or hemoglobin decrease without clear source  Other
 
Fatal?
 
 Yes  No
 
Hospitalized?
 
 Yes  No
 
Associated with hemodynamically instability?
 
 Yes  No

	
Treatment:
 
 Blood products  Surgery  Invasive procedure  Medical therapy (PCC, andexanet, etc.)

Clinically relevant non-major bleed	
 Yes  No
 
If yes, date _____ / _____ / _____ MM DD YYYY
 
Location:
 
 Intracranial  Surgical/operative site  Gastrointestinal  Genitourinary  Retroperitoneal  Pericardial  Pulmonary  Other thoracic  Musculoskeletal  Nasopharyngeal  Hematocrit or hemoglobin decrease without clear source  Other: _____
 
Hospitalized?
 
 Yes  No
 
Treatment:
 
 Blood products  Surgery  Invasive procedure  Medical therapy (PCC, andexanet, etc.)

Non-bleed adverse drug reaction	
 Yes  No
 
If yes, date _____ / _____ / _____ MM DD YYYY
 
Type of reaction:
 
 Anaphylaxis

	
 Cutaneous (rash, etc.)  Liver function abnormalities  Other: _____
 
Hospitalized?  Yes  No
 
Study drug discontinuation?  Permanent stop  Temporary stop  Not discontinued

Myocardial infarction (defined as the presence of at least 2 of the 3 following conditions: 
• The detection of a rise and/or fall of cardiac biomarkers, with at least one of the values being elevated [preferably cardiac troponin (cTn) with at least one value above the 99th percentile upper reference limit] and with at least one of the following:
(1) symptoms of myocardial ischemia;(2) new (or presumably new) significant ST-segment/T-wave changes or left bundle branch block;(3) development of pathological	
 Yes  No
 
If yes, date _____ / _____ / _____ MM DD YYYY
 
Type:  ST elevation  Non-ST elevation
 
Fatal?  Yes  No
 
Treatment:  Systemic fibrinolysis  Percutaneous coronary intervention (angioplasty, stenting, etc.)  CABG  Medical management

Q waves on ECG; (4) new loss of viable myocardium or regional wall motion abnormality by imaging; (5) identification of intracoronary thrombus by angiography or autopsy)
	

Non-MI coronary revascularization
	
 Yes  No
 
If yes, date _____ / _____ / _____ MM DD YYYY
 
Recascularization:
 
 Percutaneous coronary intervention (angioplasty, stenting, etc.)  CABG


Stroke/TIA (defined as a new, focal neurologic deficit of sudden onset, lasting at least 24 hours, not due to a readily identifiable nonvascular cause (i.e. brain tumor, trauma), as confirmed by a neurologist and neuroimaging.)
	
 Yes  No
 
If yes, date _____ / _____ / _____ MM DD YYYY
 
Confirmation (both must be present):
 
 By neurologist  By neuroimaging
 
TIA?  Yes  No
 
Stroke?  Yes  No
 
If yes, type of stroke:  Ischemic

